9.3.1 Source data

Refer to the Clinical Study Agreement for location of source data.

9.4 Study agreements

The Principal Investigator at each/the centre should comply with all the terms, conditions, and obligations of the Clinical Study Agreement, or equivalent, for this study. In the event of any inconsistency between this Clinical Study Protocol and the Clinical Study Agreement, the terms of Clinical Study Protocol shall prevail with respect to the conduct of the study and the treatment of subjects and in all other respects, not relating to study conduct or treatment of subjects, the terms of the Clinical Study Agreement shall prevail.

Agreements between AstraZeneca and the Principal Investigator should be in place before any study-related procedures can take place, or subjects are enrolled.

9.4.1 Archiving of study documents

The Investigator follows the principles outlined in the Clinical Study Agreement (CSA).

9.5 Study timetable and end of study

The end of the study is defined as 'the last visit of the last subject undergoing the study'.

The study is expected to start in 1Q2012 and to end by 1Q2013.

The study may be terminated at individual centres if the study procedures are not being performed according to GCP, or if recruitment is slow. AstraZeneca may also terminate the entire study prematurely if concerns for safety arise within this study or in any other study with ticagrelor.

10. DATA MANAGEMENT BY ASTRAZENECA OR DELEGATE

Data management will be performed by

The data collected through third party sources will be obtained and reconciled against study data.

Adverse events and medical/surgical history will be classified according to the terminology of the latest version the Medical Dictionary for Regulatory Activities (MedDRA). Medications will be classified according to the AstraZeneca Drug Dictionary. The Medical Coding Team at ICON will perform all coding.

Data queries will be raised for inconsistent, impossible or missing data. All entries to the study database will be available in an audit trail.

Approved

Date F

The data will be validated as defined in the Data Management Plan. Quality control procedures will be applied to each stage of data handling to ensure that all data are reliable and have been processed correctly.

When all data have been coded, validated, signed and locked, clean file will be declared. Any treatment revealing data may thereafter be added and the final database will be locked.

Data associated with biological samples will be transferred to laboratories internal or external to AstraZeneca.

52(60)

11. EVALUATION AND CALCULATION OF VARIABLES BY ASTRAZENECA OR DELEGATE

11.1 Calculation or derivation of efficacy variable(s)

Not applicable.

11.2 Calculation or derivation of safety variable(s)

Not applicable.

11.2.1 Other significant adverse events (OAE)

During the evaluation of the AE data, an AstraZeneca medically qualified expert will review the list of AEs that were not reported as SAEs and DAEs. Based on the expert's judgement, significant adverse events of particular clinical importance may, after consultation with the Global Patient Safety Physician, be considered OAEs and reported as such in the Clinical Study Report.

11.3 Calculation or derivation of pharmacokinetic variables

The pharmacokinetic (PK) analyses will be performed at AstraZeneca R&D. The actual sampling times will be used in the PK calculations. PK parameters will be determined using standard non-compartmental methods. The following PK parameters will be determined:

Area under the plasma concentration-time curve from zero to 8 hours post-dose (AUC_{0-8}) may be calculated.

11.4 Calculation or derivation of pharmacodynamic variable(s)

 $P2Y_{12}$ reaction units (PRU) will be measured by VerifyNowTM $P2Y_{12}$ assay. The PRU data will be presented in the following ways. The absolute PRU at each timepoint and the % $P2Y_{12}$ inhibition from BASE (PRU vs BASE PRU) at each timepoint. For analysis, the variable will be percent inhibition of the $P2Y_{12}$ receptor from baseline. It will be calculated as percent change from baseline (pre-treatment) PRU versus each timepoint post treatment.

11.4.1 Calculation or derivation of the relationship between pharmacokinetic and pharmacodynamic variables

Only data from patients in the PK/PD analysis set will be summarized and formally analysed. Graphical methods will be employed to explore possibilities for PK/PD modelling if appropriate a sigmoid E_{max} model may be used.

11.4.2 Population analysis of pharmacokinetic/pharmacodynamic variables

Not applicable.

11.5 Calculation or derivation of pharmacogenetic variables

The results will be provided in a separate report.

12. STATISTICAL METHODS AND SAMPLE SIZE DETERMINATION BY ASTRAZENECA

12.1 Description of analysis sets

12.1.1 Pharmacodynamic analysis set

The pharmacodynamics analysis set will include all patients for whom PD data was available with no major protocol deviations thought to significantly affect the pharmacodynamics of ticagrelor or clopidogrel.

12.1.2 Safety analysis set

All subjects who received at least one dose of study medication will be included in the safety population. Throughout the safety results sections, erroneously treated subjects (eg, those randomised to treatment A but actually given treatment B) will be accounted for in the actual treatment group.

12.2 Methods of statistical analyses

All data from patients included in the pharmacodynamics (PD) analysis set will be summarized using descriptive statistics by sequence, treatment, period and time relative to dose. The primary analysis of the difference between ticagrelor and clopidogrel in PRUs at 2 hours will be analyzed using a mixed effect model with terms for period (I/II, treatment (A/B), pre-dose PRU, and a random effect for patient within sequence. Treatment level means will be estimated using least squares means and 2-sided 95% confidence intervals. Tests will be evaluated with a 2-sided alpha level of 0.05. Distribution assumptions underlying the analysis will be assessed by residual plots. If the assumptions are violated, a Wilcoxon signed rank test will be used.

Secondary analyses of PRUs at other time points will be analyzed with similar mixed effects models. Analyses will be done at 0.5, 8 hours after the loading dose. Separate analyses will be done for pre-dose, 2, 8 hours after last morning dose, and 12 hours after last evening dose for ticagrelor or 24 hours after last dose of clopidogrel. There will be secondary analyses of percentage change from baseline in PRUs and of percentage inhibition of platelet aggregation.

Safety will be evaluated using the safety analysis set. Adverse events will be reported as proportions of subjects with adverse events. Adverse events that lead to discontinuation will be summarized. Clinical labs and vital signs will be reported using descriptive statistics by treatment and protocol time point.

54(60)

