12.3 Determination of sample size

The primary outcome of this study is P2Y₁₂ receptor inhibition at 2 hours, as measured by PRUs using Verify NowTM, comparing that measure after ticagrelor with that after clopidogrel. Calculations using 90% power, detection of a difference of 100 PRUs, a 2-sided alpha=0.05, and a correlation of 0.5 between paired observations yields a required sample size of 12 completed subjects. This assumes a standard deviation of 93 PRUs, which represents the largest variability for ticagrelor or clopidogrel observed in study D5130C00048 at time-points within the first 24 hours. This also assumes a correlation of 0.5 between paired observations.

Date Printed:

Based on a need to enrol a cohort of sufficient size for clinical credibility and to evaluate $P2Y_{12}$ receptor inhibition at secondary timepoints and to collect potential adverse events, we plan to obtain 28 subjects completing the study; this yields >99% power to demonstrate the anticipated effect.

The number of subjects that will agree to participate in the genetic research is unknown. It is therefore not possible to establish whether sufficient data will be collected to allow a formal statistical evaluation or whether only descriptive statistics will be generated. A statistical analysis plan will be prepared where appropriate.

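### The primary crossover model can be replaced, after it has been fitted, by a signed rank test that ignores period and pre-dose PRU

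*Protocol*

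**What the plan says.** Protocol Section 12.2 and the Statistical methods part of the Synopsis carry the same rule. PRU at 2 hours is analysed with a mixed model containing period, treatment, pre-dose PRU and a random effect for patient within sequence. On reporting: "Treatment level means will be estimated using least squares means and 2-sided 95% confidence intervals". On testing: "Tests will be evaluated with a 2-sided alpha level of 0.05". The distributional assumptions are judged from residual plots, and then: "If the assumptions are violated, a Wilcoxon signed rank test will be used".

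The paragraph on secondary time points calls for similar mixed models and does not repeat the fallback.

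Section 12.1.1 does not require both periods for entry to the pharmacodynamic analysis set, and Section 3.1 randomises 34 patients to obtain 28 evaluable. So some patients may contribute one period only.

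**The concern.** Two features of the rule cause trouble.

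- **Timing.** Residuals exist only after the model, treatment term included, has been fitted. The primary p-value can therefore be known when someone decides whether the plots look acceptable.
- **Choice of replacement.** The protocol names the substitute, so this is more than a detail left open. In a two-period crossover, a period effect enters the within-patient treatment difference with opposite signs in the two sequences. A signed rank test on those differences has no term to remove it. It also drops the pre-dose PRU adjustment that the same paragraph requires, and every patient with only one period.

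At stake are the size and precision of the reported primary effect, and whether the reported analysis was fixed in advance. Smaller contrasts at secondary time points would be exposed too, if the fallback was meant to apply there.

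**Working it through.** **1. The plan's own figure.** Section 12.3 states: "Calculations using 90% power, detection of a difference of 100 PRUs, a 2-sided alpha=0.05"; "This assumes a standard deviation of 93 PRUs, which represents the largest variability for ticagrelor or clopidogrel observed in study D5130C00048"; "This also assumes a correlation of 0.5 between paired observations"; and that this "yields a required sample size of 12 completed subjects".

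SD of the paired difference = 93 × √(2 × (1 − 0.5)) = 93 PRU. With the noncentral t for a paired test, 11 patients give 89.4% power and 12 give 92.3%. The 12 is reproduced. At the planned 28 completers, power is 99.98%, which agrees with the stated >99%.

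**2. How a period effect enters.** Let D = clopidogrel minus ticagrelor PRU within a patient, δ the true difference, and π the period-2 minus period-1 effect. Then D has mean δ − π in the sequence taking clopidogrel first and δ + π in the other. The documents give no value for π; 30 and 60 PRU are assumptions.

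**3. Balanced completers, 14/14.** The shifts cancel, but the spread that the signed rank test sees grows to √(93² + π²):

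- π = 30: √(8649 + 900) = 97.7 PRU
- π = 60: √(8649 + 3600) = 110.7 PRU

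The true standard error of the mean difference stays at 93/√28 = 17.58 PRU. To a normal approximation, true alpha is 2 × [1 − Φ(1.96 × 97.7/93)] = 3.9% for π = 30, and about 2.0% with 110.7 for π = 60. Simulation gives 3.9% and 1.8%.

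**4. Unbalanced completers, 17/11.** The mean of D shifts by π × (17 − 11)/28:

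- π = 30: 6.4 PRU
- π = 60: 12.9 PRU

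The simulated median difference moved by about 7 and 15 PRU. The period-adjusted estimate, which averages the two sequence means of D, does not move. Its standard error is 93 × √((1/17 + 1/11)/4) = 18.0 PRU.

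**5. Simulated operating characteristics.** Inputs: 28 complete pairs, difference SD 93, two-sided 0.05, an assumed true difference of 50 PRU, and 5,000 to 6,000 runs per scenario. The period-adjusted analysis is the crossover t-test on complete pairs, that is, the mixed model without the pre-dose covariate.

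| Completers | Period effect | Signed rank alpha | Signed rank power | Period-adjusted power |
|---|---|---|---|---|
| 14/14 | 30 | 3.9% | 73% | 78% |
| 14/14 | 60 | 1.8% | 61% | 78% |
| 17/11 | 30 | about 5% | 59% | 76% |
| 17/11 | 60 | about 5% | 35% | 76% |

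The 17/11 powers are for a shift that opposes the treatment effect. With no period effect, signed rank power is 76% at 14/14. At an assumed 40 PRU the pattern is the same: at 14/14 the model against the signed rank test gives 60% and 58% (no period effect), 60% and 53% (30 PRU), and 58% and 40% (60 PRU).

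**6. At the design difference of 100 PRU.** Rejection is about 100% for the period-adjusted test and 98.8% to 100% for the signed rank test in every 14/14 and 17/11 scenario run.

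**7. Single-period patients.** Adding six to 28 pairs lowers the standard error of the treatment difference from 17.58 to 17.12 PRU, or 2.6%.

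**The case against.** The strongest reply is that the damage depends on a period effect that no document suggests. Section 3.2 plans a washout meant to clear both drugs, and 60 PRU is 60% of the design difference. With no period effect the signed rank test loses almost nothing. A 17/11 split is also uncommon: if 34 were allocated 17/17 (an assumption; no ratio is stated) and six losses fell at random, all six would come from one sequence with probability 2 × C(17,6)/C(34,6) = 1.8%. The assay operator is blinded and the outcome is an instrument reading. All of this stands and limits the size of the point. It does not justify the rule: washout addresses carry-over rather than period effects in general, the plan itself puts period in the model, and blinding the operator does not govern the choice of test.

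A reader might also infer more than the documents support:

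- **That the model forces one variance on two drugs with different spread.** Section 12.2 states no residual structure. Section 12.3 gives one SD, "which represents the largest variability for ticagrelor or clopidogrel observed in study D5130C00048", without saying which drug it came from. Unequal spread would affect the intervals for the separate treatment means. The treatment contrast on complete pairs kept its level (4.5% to 5.1%) with an assumed ticagrelor SD of 40 against 93.
- **That the switch inflates the type I error.** In the simulations this needed a corner case: an 18/10 split with a 60 PRU period effect gave 8% to 9%. At 17/11 alpha stayed near 5%, and at 14/14 it fell below 5% once there was a period effect.
- **That the signed rank test yields no interval.** It inverts to a Hodges-Lehmann estimate and interval. The weakness is that this estimate is not adjusted for period.
- **That the secondary analyses certainly carry the same fallback.** The sentence closes the primary-analysis paragraph, so its reach to secondary time points is an inference.

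**Conclusion.** The point holds in a limited form. The protocol fixes a switch, made after the fit and on residual plots, from a period-adjusted model to a test that ignores period and pre-dose PRU and uses only complete pairs. If there is a period effect, that test is conservative and loses power when completers are balanced across sequences, and its estimate is shifted when they are not.

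The figures rest on 28 pairs and a difference SD of 93 PRU, which follow from Section 12.3. The period effects, the 40 and 50 PRU contrasts and the sequence splits are assumed, and the pre-dose covariate is left out. The conclusion at 100 PRU is not threatened in the 14/14 and 17/11 scenarios. The loss of single-period patients is a minor part of the cost.

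**What to change.** Delete the switch from Section 12.2 and the Synopsis. Keep the period-adjusted mixed model as the primary analysis whatever the residual plots show. Always report, as a sensitivity analysis, the crossover rank test: a Wilcoxon rank-sum test comparing within-patient period differences between the two sequences, with the Hodges-Lehmann estimate and confidence interval. Use the same approach at secondary time points if the fallback was meant to apply there. Treatment-specific residual variances may be added as an option; they matter only for the intervals around the separate treatment means.

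The cost is protocol wording and a few lines of code. The rank-sum test is itself unadjusted for pre-dose PRU and also needs both periods. With no period effect it is slightly less powerful than the signed rank test at an assumed 50 PRU: about 75% against 76% at 14/14, and 74% against 76% at 17/11. That is acceptable for a sensitivity analysis.

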12.2.1 Outcome variables

12.2.1.1 Pharmacodynamic outcome variables

- Primary outcome variables:

- Inhibition of the P2Y₁₂ receptor at 2 hours after loading dose with ticagrelor compared with clopidogrel as measured by PRU from Verify Now[™] in Hispanic patients.

- Secondary outcome variables:

-Inhibition of the P2Y₁₂ receptor at 0.5 and 8 hours after loading dose with ticagrelor compared with clopidogrel as measured by PRU from Verify NowTM in Hispanic patients.

-Inhibition of the P2Y₁₂ receptor at 2 hours, 8 hours and end of dosing interval after 7 days of administration with ticagrelor compared with clopidogrel as measured by PRU from Verify NowTM in Hispanic patients.

Percent reduction in platelet P2Y₁₂ receptor activity measured by VerifyNowTM on P2Y₁₂ reaction units (PRU) measured by VerifyNowTM P2Y₁₂ assay, represented as percentage change from baseline (pre-treatment)

% Reduction from baseline =
$$\left(1 - \left[\frac{\text{PRU after study drug}}{\text{PRU at baseline}}\right]\right) \times 100\%$$

- Percentage inhibition of platelet aggregation as measured by Verify Now™ measured as change from BASE (on-treatment)

12.2.1.2 Safety outcome variables

- Adverse events, physical examination and vital signs

12.2.2 Interim analyses

An interim analysis will not be performed.

12.3 Determination of sample size

The primary outcome of this study is P2Y₁₂ receptor inhibition at 2 hours, as measured by PRUs using Verify NowTM, comparing that measure after ticagrelor with that after clopidogrel. Calculations using 90% power, detection of a difference of 100 PRUs, a 2-sided alpha=0.05, and a correlation of 0.5 between paired observations yields a required sample size of 12 completed subjects. This assumes a standard deviation of 93 PRUs, which represents the largest variability for ticagrelor or clopidogrel observed in study D5130C00048 at time-points within the first 24 hours. This also assumes a correlation of 0.5 between paired observations.

Date Printed:

Based on a need to enrol a cohort of sufficient size for clinical credibility and to evaluate $P2Y_{12}$ receptor inhibition at secondary timepoints and to collect potential adverse events, we plan to obtain 28 subjects completing the study; this yields >99% power to demonstrate the anticipated effect.

The number of subjects that will agree to participate in the genetic research is unknown. It is therefore not possible to establish whether sufficient data will be collected to allow a formal statistical evaluation or whether only descriptive statistics will be generated. A statistical analysis plan will be prepared where appropriate.

12.4 Data monitoring committee

A data monitoring committee will not be used for this study.

13. IMPORTANT MEDICAL PROCEDURES TO BE FOLLOWED BY THE INVESTIGATOR

The principal investigator(s) is responsible for ensuring that procedures and expertise are available to handle medical emergencies during the study. A medical emergency usually constitutes an SAE and should be reported as such. In the case of a vascular event, the patients should be discontinued from the study if administration of a prohibited concomitant medication treatment with PCI or CABG or other major surgery is needed.

The AstraZeneca representative will work with the investigator to compile all the necessary information and ensure that the appropriate AstraZeneca Patient Safety Department receives a report by day one for all fatal and life-threatening cases and by day five for all other SAEs.

All Serious Adverse Events (SAE) must be reported to Clinical Patient Safety, AstraZeneca Marketing Company within one day (that is immediately but not later than the end of the next business day) by fax. Clinical Drug Safety will forward the SAE report to the applicable AstraZeneca R&D. The monitor should also be informed when an SAE has occurred.

Follow-up information on SAEs must also be reported by the investigator within the same time frames.

The investigator and/or Sponsor are responsible for informing the Ethics Committee and/or the Regulatory Authority of the SAE as per local requirements.

For Serious Adverse event reporting, complete the SAE report and fax the report to the appropriate Patient Safety department.

There is no known antidote to reverse the effects of ticegrelor. The average half-life of ticegrelor is approximately 12 hours, so blood levels of ticegrelor should be low by 48 to 72 hours (ie, 4 to 6 half-lives) after discontinuation. Platelet transfusions may be given. It is not known if new platelets may be inhibited by ticagrelor as long as it is circulating in blood.

PLEASE CHECK ITS VALIDITY BEFORE USE

A PRINTED COPY OF AN ELECTRONIC DOCUMENT.

5 H

THIS

13.1 Major bleeding events

Major bleeding events should be managed according to accepted standard of care.

If a patient experiences a major bleed as defined in Section 6.4.6.1, study drug should usually be discontinued but may be resumed at the discretion of the investigator provided the cause of bleeding has been identified and controlled.

13.2 Minor bleeding events

If a patient experiences a minor bleeding event as defined in Section 6.4.6.1, study drug may be continued, interrupted temporarily or discontinued permanently at the discretion of the investigator.

13.4 Overdose

- An overdose with associated AEs is recorded as the AE diagnosis/symptoms on the relevant AE modules in the CRF and on the Overdose CRF module.
- An overdose without associated symptoms is only reported on the Overdose CRF module.

If an overdose on an AstraZeneca study drug occurs in the course of the study, then investigators or other site personnel inform appropriate AstraZeneca representatives **within one day**, ie, immediately but no later than **the end of the next business day** of when he or she becomes aware of it.

The designated AstraZeneca representative works with the investigator to ensure that all relevant information is provided to the AstraZeneca Patient Safety data entry site.

For overdoses associated with SAE, standard reporting timelines apply, see Section 6.4.4. For other overdoses, reporting should be done within 30 days.

13.5 Pregnancy

All outcomes of pregnancy should be reported to AstraZeneca.

Women recruited into the study must be either post-menopausal or surgically sterile.

If a patient becomes pregnant, the patient should be discontinued from the study treatment and attend an End Of Treatment visit and be followed until study closure.

Pregnancy itself is not regarded as an AE unless there is a suspicion that the investigational product under study may have interfered with the effectiveness of a contraceptive medication.

However, the outcome of all pregnancies (spontaneous miscarriage, elective termination, normal birth or congenital abnormality) must be followed up and documented even if the patient was discontinued from the study.

All reports of congenital abnormalities/birth defects are SAEs. Spontaneous miscarriages should also be reported and handled as SAEs. Elective abortions without complications should not be handled as AEs. All outcomes of pregnancy must be reported to AstraZeneca on the "Pregnancy Outcomes Report" form.

